Official Title of the study:

Evaluation of the efficacy of probiotics in treating constipation in elderly patients with multiple chronic co-morbidities: a randomized control trial

NCT no: Nil

Date of Document:

22nd July 2019

Study Protocol

1. Study design

This is a randomized double-blinded clinical trial study.

2. Study population and subjects

Background and selection of study centers

The study will be conducted at the outpatient clinics, medical and surgical wards in Universiti Kebangsaan Malaysia Medical Centre.

3. Target population

- 3.1 The target populations are older patients aged 60 years or above with at least 2 chronic medical illnesses (Appendix A) and who complain of constipation that persists for several weeks or longer.
- 3.2 These patients are those who attending the medical/surgical outpatient clinics or being admitted to the medical/surgical wards in UKM Medical Centre during the study period.

The participants will be assigned to either interventional group or control randomly and the random selection is pre-determined prior to recruitment.

4 Inclusion criteria.

- 4.1 Elderly patients aged 60 years or above and able to give consent.
- 4.2 Patients who complain of constipation as per Mayo's clinic definition:
"Infrequent bowel movements of fewer than three bowel movements per week or difficult passage of stools that persists for several weeks or longer". (13)
- 4.3 Patients who have at least 2 chronic illnesses such as Diabetes Mellitus, Hypertensions, Chronic Kidney disease, Chronic Lung disease, or any medical illness which are prone to have constipation.

5. Exclusion criteria.

- 5.1 Patients with constipation of organic cause such as colorectal carcinoma, colonic ischaemia, inflammation, post radiation stricture, obstruction or presence of external compression.
- 5.2 Patients with constipation of neurological causes such as cerebrovascular disease and stroke, Parkinson's disease, autonomic neuropathy and spinal cord lesions.
- 5.3 Patients who are taking calcium supplements more than 1500mg a day.
- 5.4 Patients who are immune-compromised or critically ill.
- 5.5 Patients who are on opioid analgesia.
- 5.6 Patients with psychiatric illness.
- 5.7 Patients who are on any form of medications at point of entering the study that altered the normal bowel movement (either decreasing or increasing the peristalsis of the gut)
- 5.8 Patients who refuse to enter or consent for the study.

6. Subject withdrawal and Drop out

Subjects will be withdrawn from the study in the event of:

1. Consent is withdrawn by the patient.
2. Patients will be withdrawn from the study if they experience intolerable or excessive side effects due to the probiotics.

Subject drop out is predicted at 10% and is taken into consideration in the sample size calculation.

7. Study Intervention

Patient will be randomized into a treatment or control group. No other treatments such as laxatives or enemas are given to all patients.

1. Treatment group.
 - a. Each patient will receive probiotics in form of granular powdered microbial cell preparation (Hexbio®) – Specialized formulation of six microbial strains containing:
 - i. Lactobacillus acidophilus BCMC® 12130
 - ii. Lactobacillus casei BCMC® 12313
 - iii. Lactobacillus lactis BCMC® 12451

- iv. Bifidobacterium bifidum BCMC® 02290
- v. Bifidobacterium infantis BCMC® 02129
- vi. Bifidobacterium longum BCMC® 02120

b. Dosage: 1 sachet twice a day after meals for 1 week.

2. Control group

- a. Each patient will receive placebo sample of similar appearance and composition but do not contain probiotics.

8. Efficacy, Safety and Other Assessments

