8.1 Primary end point

A completed questionnaire on patient's demographic and medical illness data, stool output/day, stool consistency per output/day and constipated related symptoms scoring/day over the period of 7 study days.

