8.2 Safety

Patients will be counseled that generally safety profile of probiotics seems to be good. Based on the available trials, no adverse effects were noted. There might be a concern issue of safety in immune-compromised patients or those critically ill, which they will be excluded in this study.

Patients will be withdrawn from the study if they experience intolerable or any possible excessive side effects due to probiotics.

9. Assessment variables and methods of assessing.

9.1 Targeted patients will be assessed with a questionnaire (Appendix C) on gastrointestinal symptoms, well-being and stool habits. The stool consistency will be scored by a seven-point scale according to the Bristol Stool Form Scale (Appendix B). Severity of constipation will be categorized into four groups (severe, moderate, mild and no symptoms). Symptoms specifically

related to constipation such as bloating and flatulence will be recorded in detail. Severity of symptom is measured by Likert score of frequency (Very frequently, frequently, occasionally, rarely and never).

9.2 Each individual patient will be required to fill in the questionnaire at the beginning of the trial. Subsequently, patient will be required to fill up the stool chart and recorded their symptoms in a given dairy daily during the study period. Training on how to use and record the dairy will be conducted upon embarking into the study. A contact number will be advised to the participants to aid their understanding. The dairy will be collected at day 7 upon completion of the study.

Other assessment

1. Assessment of the presence of underlying medical illness will be done at the initial presentation, assessed by questionnaire about the medical history and physical examination.

10. Study conduct

10.1 Elderly patients attending medical/surgical clinics or being admitted to the medical/surgical wards PPUKM will be screened. Those with underlying medical illnesses and suspected to have constipation are selected. Random selection of the participants either for intervention group or control will be pre-determining during screening.

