APPENDIX C

EVALUATING THE EFFECT OF PROBIOTICS IN CHRONIC CONSTIPATION ELDERLY PATIENTS WITH MULTIPLE CO-MORBIDITIES

Data Collection Form

Study Number:

Patient's Sticker:

Socio-demography:

Age:

Gender: Male / Female

Ethnic : Malay / Indian / Chinese/ Others (please state: _____)

Clinical characteristic

Medical illness:

If yes, please tick:

	Durations (years)
Diabetes Mellitus	()
Asthma	()
Hypertension	()
Dyslipidaemia	()
Chronic Kidney disease	()
Others (please specify): _____	()
	()

Symptoms associated with constipation:

(*at least in 25% of defecations – Rome III diagnostic criteria of functional constipation)

If yes, please tick:

Straining	()
Lumpy or hard stools	()
Sensation of incomplete evacuation	()
Sensation of anorectal obstruction/ blockage	()
Manual maneuvers to facilitate defecations	()
Fewer than 3 defecations per week	()

Duration: _____ months/ years

Previous treatment:

frequency:

Laxatives	()	() days/months/years
Probiotics	()	() days/months/years
High fibre diets	()	() days/months/years
Enemas	()	() days/months/years

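### Ward and clinic patients are pooled, but setting is not a stratum, not a field on the forms and not in the analysis; recording it and stratifying the tests would be a cheap gain in precision

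*Combined protocol and SAP*

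**What the plan says.** **Recruitment.** Section 3.2 defines the target population as patients "attending the medical/surgical outpatient clinics or being admitted to the medical/surgical wards in UKM Medical Centre during the study period". Section 10.1 sends both groups through one screening route: "Elderly patients attending medical/surgical clinics or being admitted to the medical/surgical wards PPUKM will be screened".

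**Allocation.** Section 3 states: "The participants will be assigned to either interventional group or control randomly and the random selection is pre-determined prior to recruitment". Section 7 adds "Patient will be randomized into a treatment or control group", and section 10.1 says "Random selection of the participants either for intervention group or control will be pre-determining during screening". None of these names a stratification factor, a block scheme, minimisation or an allocation ratio.

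**Forms.** The socio-demographic part of Appendix C asks for age, gender and ethnicity ("Ethnic : Malay / Indian / Chinese/ Others (please state"). The rest covers illnesses, constipation symptoms and previous treatment. Appendix D and the daily diary in Appendix B cover bowel habit and symptoms. As reproduced, none has a field for ward or clinic, or for discharge during the week. Each has a box for a patient sticker.

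**Outcome and analysis.** Section 8.1 lists daily stool output, stool consistency and "constipated related symptoms scoring/day over the period of 7 study days". The statistical analysis plan compares improvement in stool frequency and consistency by Mann-Whitney U and symptom improvement by chi-squared. It has no covariate, stratum or subgroup, and does not list the baseline variables to be compared.

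**The concern.** Follow-up is a single week. During that week an admitted patient may be recovering from acute illness, eating hospital food, moving less, starting new medicines or going home, and any of these could change bowel habit whichever sachet is taken. A clinic patient is less exposed to them. If the average 7-day change does differ by setting, two things follow.

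- The difference sits inside the outcome variance of an unstratified test, so power is lost.
- If one arm happens to contain more ward patients, the observed arm contrast moves by the imbalance times the setting difference. With no field for setting, nobody reading the trial data could see this or correct for it.

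**Working it through.** There is no figure in the plan to reproduce. Section 6 mentions a sample size calculation, but the text gives no sample size, power, effect size or SD. Everything below therefore rests on assumptions that are not in the documents: 1:1 simple randomisation, two-sided alpha of 0.05, normally distributed change with within-setting SD 1, and a setting difference in 7-day change of 0.5 or 1.0 SD. The inpatient share is 50%, with 30% also tried for the imbalance.

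**1. Size of chance imbalance.** With half the patients inpatients, the SD of the arm difference in inpatient share is sqrt(2 × 0.25 / n), with n per arm. The 95% limits are 1.96 times this:

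- n = 30: 1.96 × 0.129 = 0.253
- n = 50: 1.96 × 0.100 = 0.196
- n = 75: 1.96 × 0.082 = 0.160

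Multiplied by a 1.0 SD setting difference, the arm contrast shifts by 0.25, 0.20 or 0.16 SD at those limits; for 0.5 SD, halve these. They are 95% limits, not maxima. Simulated over inpatient shares of 30% and 50%, an imbalance of at least 20 points occurs in 16–20% of allocations at 25 per arm, 4–6% at 50, 1–2% at 75 and under 1% at 100.

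**2. Variance cost.** With half inpatients, pooling raises the outcome SD by sqrt(1 + 0.25 × d²), where d is the setting difference in SD units. This is sqrt(1.0625) = 1.031 for d = 0.5 and sqrt(1.25) = 1.118 for d = 1.0. For a normal test with 80% power without the setting difference, the power becomes:

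- d = 0.5: Φ(2.802/1.031 − 1.96) = Φ(0.758) = 0.78, a loss of about 2 points
- d = 1.0: Φ(2.802/1.118 − 1.96) = Φ(0.546) = 0.71, a loss of about 9 points

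**3. Simulation of the planned test against a stratified one.** There were 6,000 runs per scenario. Allocation was simple in every run; only the analysis differed (plain Mann-Whitney U or van Elteren by setting). The product effect was (1.96 + 0.842) × sqrt(2/n), that is 0.79, 0.56 and 0.40 SD for 25, 50 and 100 per arm.

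| n per arm | d | Type I, plain | Type I, stratified | Power, plain | Power, stratified | Gain (points) |
|---|---|---|---|---|---|---|
| 25 | 0.5 | 0.049 | 0.048 | 0.748 | 0.759 | 1.1 |
| 50 | 0.5 | 0.052 | 0.050 | 0.734 | 0.757 | 2.3 |
| 100 | 0.5 | 0.052 | 0.052 | 0.753 | 0.779 | 2.6 |
| 25 | 1.0 | 0.048 | 0.050 | 0.666 | 0.753 | 8.7 |
| 50 | 1.0 | 0.050 | 0.047 | 0.682 | 0.764 | 8.2 |
| 100 | 1.0 | 0.049 | 0.048 | 0.671 | 0.774 | 10.3 |

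The gains agree with step 2 and come from the analysis alone.

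**4. Given an unlucky allocation** (imbalance of at least 20 points, 25 or 50 per arm), the plain test has a conditional false-positive rate of 0.06–0.09 at d = 0.5 and 0.09–0.20 at d = 1.0. If the imbalance works against a real effect, power falls to 0.60 (n = 25) or 0.48 (n = 50) at d = 0.5, and to about 0.30 at d = 1.0. If it works in favour, the rejection rate is 0.85–0.97. At 100 per arm such imbalances were too rare to estimate these rates reliably.

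The chi-squared analysis of symptoms was not simulated.

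**The case against.** The strongest reply is that randomisation already deals with this. Any prognostic factor, recorded or not, can be unbalanced by chance, and the test's error rate allows for it. That stands: in the table the planned test keeps type I error at 0.048–0.052 whatever the setting difference. A reader might infer that pooling the settings biases the comparison or makes a false-positive result more likely overall. It does neither. The rates in step 4 of the working apply only to an allocation already known to be unbalanced.

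A reader might also take it as established that ward and clinic patients change differently over 7 days. The documents do not say so and give no figure. Several rules narrow the possibility: constipation must already have lasted some weeks (3.1, 4.2); critically ill patients, opioid users and patients on bowel-active drugs at entry are excluded (5.4, 5.5, 5.7); and no laxatives or enemas are given (section 7). Diet, mobility, discharge and drugs started after entry remain open, so the premise is plausible but unproven.

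Nor do the documents support saying that setting is unrecoverable. The patient sticker may link to hospital records, and the flow chart and parts of Appendix D could not be read. What can be said is that the reproduced forms have no field for it.

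Finally, large imbalances become uncommon at about 75 per arm and above. That is true, but no sample size is visible, so it offers no assurance here.

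**Conclusion.** The point holds as a low-cost improvement, not as an error in the plan. The two settings are pooled, and setting is not used in allocation, data collection or analysis. If 7-day change depends on setting, the expected cost is precision: roughly 1–3 points of power at a 0.5 SD difference and 8–10 at 1.0 SD. In addition, an unlucky allocation could not be recognised or adjusted for from the trial's own forms. If change does not depend on setting, nothing is lost. The size rests on the assumed setting difference, inpatient share, 1:1 ratio, normal outcomes and arm sizes of 25 to 100, none of which the documents supply. The stronger readings, inflated type I error or systematic bias, are not supported.

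**What to change.** 1. Add a field to Appendix C, completed at randomisation: recruited from ward / clinic.
2. Name setting among the baseline variables and report it by arm.
3. In the statistical analysis plan, replace the plain tests with setting-stratified ones: van Elteren for stool frequency and consistency, Cochran-Mantel-Haenszel for symptom improvement.
4. Where feasible, use separate blocked allocation lists for ward and clinic patients. Items 1 to 3 are worth having without this.
5. Discharge day may be recorded for description. It arises after randomisation, so it should not be a stratum or covariate.

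The cost is one more form field and slightly more analysis work, with no extra patients or visits. In the simulations the stratified rank test kept type I error at 0.047–0.052. If two lists are used, blinded product and placebo supplies must also be kept to each list, which is more than a second sheet of paper but still modest.

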10.2 A written consent is obtained. (Appendix E)

10.3 The patients' demographic data and medical history will be obtained by conducting an interview and a physical examination.

10.4 In the first interview, patient will also be asked to complete a questionnaire on the gastrointestinal symptoms, stool consistency and severity of constipation.

Patients will be given 7 days' supply of placebo or probiotics, which patient are required to take each sachet of Hexbio® or placebo twice per day for 7 days.

10.5 A training of using the daily stool dairy will be done at the beginning of study. Upon completion (day 7) the dairy will be collected and data will be analyzed.

FLOW CHART

[figure not shown]

Figure 1. Flow chart of the study methodology.

GLOSSARY OF TERMS

1. Probiotics

Living microorganisms that enter the gastrointestinal tract in an active form in sufficient numbers to exert positive effect.

2. Constipation

A condition in which there is difficulty in emptying the bowels, usually associated with hardened feces.

3. Functional Constipation

A condition that fulfill the **Rome III criteria for functional constipation**.

Refer to Appendix A

4. Bristol Stool

A medical aid designed to classify the form of human feces into seven categories. Refer to Appendix B

5. Advanced Chronic Illness

An occurring when one or more conditions become serious enough that general health and functioning decline, and treatments begin to lose their impact.

6. Colony Forming Unit (CFU)

[figure not shown]
A unit used to estimate the number of viable bacteria or fungal cells in a sample.

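### The plan does not say whether the exclusion for immune compromise and critical illness applies after entry, and its withdrawal list does not cover a patient who reaches either state during days 1–7 for reasons not attributed to the product

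*Combined protocol and SAP*

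**What the plan says.** Section 5.4 lists among the exclusions "Patients who are immune-compromised or critically ill". Section 8.2 gives the reason: "There might be a concern issue of safety in immune-compromised patients or those critically ill, which they will be excluded in this study". It names no other specific hazard and otherwise reassures: "Based on the available trials, no adverse effects were noted".

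Section 6 gives two grounds for withdrawal. The first is "Consent is withdrawn by the patient". The second is "Patients will be withdrawn from the study if they experience intolerable or excessive side effects due to the probiotics". Section 8.2 repeats the second ground in somewhat wider words: "Patients will be withdrawn from the study if they experience intolerable or any possible excessive side effects due to probiotics".

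Section 10.4 tells patients to "take each sachet of Hexbio® or placebo twice per day for 7 days". Section 3.2 makes inpatients eligible, since the target population includes those "being admitted to the medical/surgical wards in UKM Medical Centre during the study period". Section 3.1 requires age 60 or above and at least two chronic illnesses. The glossary defines probiotics as live organisms.

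The Statistical Analysis Plan calls its approach intention to treat, but analyses only participants who received and finished their allocated treatment. It leaves out those who were non-compliant or withdrew consent.

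**The concern.** The plan identifies two patient states in which the live product might be a concern, and its only stated answer is to keep such patients out. That answer is complete only if nobody enters either state after enrolment. The trial recruits older, multimorbid patients, some of them already in hospital, so a change of state within a week is foreseeable.

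Two things are at stake. The first is safety. If the text is followed as written, a patient who develops, say, a severe infection judged unrelated to the product meets neither withdrawal ground, while the 7-day instruction stands. The second is interpretation. The text of the diary and forms (Appendices B to D) shows no place to record such an event, its date, or when and why the product was stopped. The analysis rule would also probably drop the patient from the comparison, for a reason connected with how ill the patient became.

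**Working it through.** The plan states no figure on this point, so there is nothing to reproduce. The check is mainly a comparison of passages.

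**Step 1: the text before and after entry**

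| Question | At entry | During days 1–7 |
|---|---|---|
| Immune compromise or critical illness | Excluded (5.4), with the reason in 8.2 | Not addressed in 6, 8.2 or 10 |
| Side effects attributed to the probiotics | Not applicable | Withdrawal (6 and 8.2) |
| Patient no longer consents | Excluded (5.8) | Withdrawal (6) |
| Product intake | Not applicable | Twice daily for 7 days (10.4), with no stated condition for stopping early |

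The first row has no entry for days 1–7. No passage provides for checking 5.4 again after enrolment.

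**Step 2: which patients fall in the gap**

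- If the deterioration is attributed to the product, the side-effect ground applies. The wording in 8.2 may also reach a deterioration only possibly due to the product.
- If the patient withdraws consent, section 6 applies. A critically ill patient may be unable to do this.
- If the deterioration is put down to something else, neither ground applies. This is the gap.

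**Step 3: an illustration of size**

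The documents give no rate, sample size, ward share or allocation ratio, so every input here is an assumption:

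- rate p of reaching a 5.4 state within 7 days: 0.5% to 3% of ward patients;
- ward patients in the trial: 50;
- allocation 1:1, so m = 50 × 1/2 = 25 on probiotic;
- patients independent of one another.

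Expected number on probiotic = m × p:

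- 25 × 0.005 = 0.125
- 25 × 0.03 = 0.75

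Chance of at least one on probiotic = 1 − (1 − p)^m:

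- 1 − 0.995^25 = 0.118, about 12%
- 1 − 0.97^25 = 0.533, about 53%

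Only the probiotic arm is counted, because section 7 says the placebo contains no probiotics.

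**The case against.** The strongest reply is that this is silence, not contradiction. An exclusion list and a withdrawal list answer different questions. Section 10.4 is an ordinary dosing instruction and does not say that intake continues whatever happens. Treating clinicians might well stop the product, exposure lasts only a week, and the flow chart and consent pages, which could not be seen, may address stopping. Much of this stands, and it rules out several stronger readings that a reader might infer:

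- **That the plan keeps a deteriorating patient on the sachets.** No passage says so. It is the default when 6 and 10.4 are read literally.
- **That 5.4 is an entry-only rule.** Criterion 5.7 is expressly tied to the moment of entry, whereas 5.4 and 8.2 carry no time limit and could be read as covering the whole study. Nothing in 6 or 10 puts that reading into effect, so the fair description is an ambiguity.
- **That safety protection ends at enrolment.** Sections 6 and 8.2 both withdraw enrolled patients for side effects.
- **That the plan calls these states unsafe.** Section 8.2 says only that there might be a concern.
- **That the chance of a case is far higher.** Counting both arms under the same assumed rates gives 1 − 0.995^50 = 22% to 1 − 0.97^50 = 78% for 50 ward patients. That includes placebo patients, who receive no live organisms.

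The reply does not close the gap. A safety criterion with two tenable readings, one of which the withdrawal list does not support, needs clarifying. Stops left to individual judgement would also have no visible place on the forms.

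**Conclusion.** The point holds in a limited form. The plan raises a possible safety concern about two patient states, relies on exclusion to meet it, and does not say whether that applies after entry. A ward patient who reaches either state during days 1–7, for reasons not attributed to the product, falls outside both withdrawal grounds.

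How often this would happen cannot be determined from the documents. The 12% to 53% is conditional on the assumed rate, ward numbers and allocation. It is the chance that at least one probiotic patient reaches such a state, not the chance that dosing then continues or that harm follows. The case for acting rests on the inconsistent treatment of a concern the plan itself raises and on the low cost of correction, not on that percentage.

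**What to change.** 1. Reconcile 5.4 and 8.2 with 6 and 10.4 so that the plan treats immune compromise and critical illness consistently at entry and during days 1–7. What the rule should be is for the investigators and the ethics committee to decide.
2. Add a dated yes/no field for a 5.4 condition arising during days 1–7.
3. Whatever rule is chosen, keep these patients in follow-up and in the randomised comparison. This means changing the Statistical Analysis Plan text that restricts the analysis to those who finished their allocated treatment.

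The cost is a short protocol amendment, one form field and a revised sentence or two in the analysis plan. The downside is that the comparison may include a few more patients with incomplete product exposure.

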APPENDIX B

DAILY STOOL DIARY						LIKERT SCALE / NUMERIC PAIN RATING SCALE							
Study No: _____ Patient's Sticker: _____ EVALUATING THE EFFECT OF PROBIOTICS IN CHRONIC CONSTIPATION ELDERLY PATIENTS WITH MULTIPLE CO-MORBIDITIES													
DAY	CONSTIPATION RELATED SYMPTOMS					BRISTOL STOOL CHART							
	STRAINING	PAINFUL EVACUATION	BLOATING & FLATULENCE	STOMACH CRAMPS	OTHERS		TYPE 1	TYPE 2	TYPE 3	TYPE 4	TYPE 5	TYPE 6	TYPE 7
BEFORE													
1													
2													
3													
4													
5													
6													
7													

Instructions: Please fill up the boxes according to likert scale for the constipation related symptoms and mark 'X' for the Bristol stool chart.

Bristol chart adapted from http://www.cbc.ca/stevenandchris/content/images/poop_101_1.jpg

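### Patients with intolerable side effects leave the study, not just the sachets, and no readable text plans their diary afterwards: a cheap improvement, to be made together with the SAP analysis set

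*Combined protocol and SAP*

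**What the plan says.** Section 6 lists two grounds for leaving the study: withdrawn consent and side effects. On the second it says: "Patients will be withdrawn from the study if they experience intolerable or excessive side effects due to the probiotics". Section 8.2 says it again: "Patients will be withdrawn from the study if they experience intolerable or any possible excessive side effects due to probiotics". Neither section offers stopping the sachets while staying under observation.

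The outcome in section 8.1 includes "constipated related symptoms scoring/day over the period of 7 study days". Section 9.2 has the patient chart stools and says they "recorded their symptoms in a given dairy daily during the study period". On collection, section 9.2 says "The dairy will be collected at day 7 upon completion of the study" and section 10.5 says "Upon completion (day 7) the dairy will be collected and data will be analyzed". No readable text describes an early return of the diary or any recording after withdrawal. The flow chart is not shown and the consent pages were removed, so this statement covers the readable text only.

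Section 6 predicts 10% drop-out without splitting it by reason or arm. The SAP calls its analysis intention to treat, but restricts it to participants who received and finished their assigned treatment. It leaves out those who were non-compliant or withdrew consent.

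**The concern.** A patient who leaves the study on day 3 has no stated duty to record days 4 to 7, or to hand in days 1 to 3. The diary in Appendix B scores "BLOATING & FLATULENCE", stomach cramps and painful evacuation. These are outcomes, but they are also plausible reasons to stop a gut product. The missing days could therefore depend on the outcome and, through it, on the arm.

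The current SAP omits these patients altogether, which is a separate and larger problem. Once that is corrected, something must stand in for the days never recorded. Carrying forward the last recorded days would overstate symptoms if complaints settle after stopping, and would count against the arm with more withdrawals. Omitting the patients would tend to flatter that arm. Days not recorded in a 7-day diary cannot be reliably rebuilt later.

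**Working it through.** **Plan figures.** There is none to reproduce: the documents give no sample size, power, effect size or standard deviation. The 10% all-cause drop-out (section 6), the 7-day window (section 8.1) and the 0.05 level (SAP, sidedness not stated) are the only usable inputs.

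**Text, side by side.** Withdrawal is from the study (6, 8.2); recording is during the study period (9.2); collection is at day 7 on completion (9.2, 10.5). Together these leave no provision for days after withdrawal. Loss is an inference from the three, not a statement in any of them.

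**Days lost per patient.** A stop at the end of day k leaves 7 − k days: 6 of 7 (86%) for k = 1, down to 1 of 7 (14%) for k = 6.

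**Illustration.** All of the following are assumptions: the SAP set is corrected; half the 10% drop-out is for side effects (5% on average); the split is 2:1, so 6.7% v 3.3%; 3 to 5 days are lost; pre-withdrawal days are returned and used; 50 or 100 patients per arm; two-sided testing.

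- Diary days lost: 0.05 × 3/7 to 0.05 × 5/7 = 2.1% to 3.6%.
- Excess loss between arms: 2/30 − 1/30 = 0.0333.
- Stool outcomes, with a gap of 0.5 to 1.0 SD between the unrecorded days and whatever stands in for them: bias = 0.0333 × (3/7 × 0.5) to 0.0333 × (5/7 × 1.0) = 0.007 to 0.024 SD. Dividing by √(2/n) gives a z shift of 0.036 to 0.119 (n = 50) or 0.051 to 0.168 (n = 100). The error rate is 5.01–5.16% or 5.03–5.33%.
- Symptom improvement, taken as yes/no with 50% improved, and these patients' proportion misstated by 25 to 50 points: bias = 0.0333 × 0.25 to 0.0333 × 0.50 = 0.8 to 1.7 points. Dividing by √(0.5/n) gives a z shift of 0.083 to 0.167 or 0.118 to 0.236. The error rate is 5.08–5.32% or 5.16–5.64%.
- If the diary is not returned at all, the stool fraction becomes 7/7: bias 0.0333 × 0.5 to 0.0333 × 1.0 = 0.017 to 0.033 SD. The z shifts, and so the error rates, equal those in the symptom line.
- With the same proportion lost and the same misstatement in each arm, every bias above is zero.

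**Checks on the actual tests.** Simulated Mann-Whitney error (20,000 runs) was 4.7–5.0% against 4.8% with no loss (n = 50), and 4.9–5.4% against 5.2% (n = 100): no clear change. Exact uncorrected chi-squared error rises from 5.69% to 5.77–6.00% (n = 50) and from 5.60% to 5.76–6.25% (n = 100), a rise of about 0.1 to 0.7 points.

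**Bounds.** For a yes/no outcome, best/worst bounds on the between-arm difference are as wide as the two missing proportions added: 6.7 + 3.3 = 10 points, or 1 + 1 = 2 points if 1% per arm is missing. For scale, the 95% confidence half-width at 50% improved is 1.96 × √(0.5/n) = 19.6 points (n = 50) or 13.9 points (n = 100).

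**The case against.** The strongest reply is that the point has no effect of its own. The SAP discards these patients whatever section 6 says, so the harm appears only after another fault is fixed. That stands, and it is why the two changes belong in one amendment.

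The size is also weak. Every input beyond the 10% is assumed, and what the documents do say points low: section 8.2 states "Based on the available trials, no adverse effects were noted", and the course lasts one week. At 50 per arm the rise in chi-squared error is smaller than the 0.69-point excess that the uncorrected test has with no loss at all. With a continuity correction the error stays below 5% throughout (3.6–4.5%). If stopping averages 1%, split 2:1, the uncorrected rise is at most 0.03 points. All of this stands.

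The documents do not settle whether pre-withdrawal days come back, nor do they define a day-7 symptom endpoint. The illustration therefore depends on choices the plan has not made. The flow chart or consent form might also provide for follow-up.

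Keeping the diary has its own risk: days after rescue laxatives could credit the arm with more withdrawals. This calls for a stated sensitivity analysis. It is not a reason to leave the days unrecorded.

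**Conclusion.** The point holds as a cheap improvement. The readable plan ends participation when the product is stopped for side effects and makes no provision for the diary afterwards, so some or all of those patients' 7-day data may be lost.

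A reader might infer that the rule by itself biases the result, or materially inflates the false-positive rate. The documents do not support this. They give no rate of side-effect withdrawal and no split by arm, so neither direction nor size is fixed. Under the assumptions above the effect is near nil for the Mann-Whitney outcomes and at most about 0.7 points of error for the chi-squared outcome. A reader might also infer that withdrawing patients for safety is itself wrong; it is not, and the threshold for stopping the product need not change.

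The case rests on avoidable uncertainty: bounds of 2 to 10 points under assumed losses, which continued diaries would narrow. It matters only if the SAP's analysis set is corrected too.

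**What to change.** Make one amendment with two parts.

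- **Protocol, sections 6 and 8.2.** Patients with intolerable or excessive side effects stop study product. Unless they withdraw consent, they stay in the study, keep the diary to day 7 and return it. Record the stop date, the reason and any laxative or enema use. Section 7 gives no such treatment, so say what is allowed after stopping.
- **SAP.** Analyse all randomised patients in their assigned arm, using all recorded days. Add a sensitivity analysis for days after rescue treatment: count the patient as not improved for the chi-squared symptom outcome, and assign the worst rank for the Mann-Whitney stool outcomes. Give best/worst bounds for days still missing.

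The cost is this wording and a few lines on the diary or data form; the existing diary and day-7 collection are reused. At an assumed 50 per arm and 5% stopping, 50 × 0.05 = 2.5 patients per arm would record 3 to 5 more days each, about 8 to 13 diary days per arm. Some of those days may reflect rescue treatment.

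The SAP is written in the past tense, so data collection may be over; the documents do not settle this. In that case report withdrawals by arm, day and reason, and include the recorded days by randomised arm with bounds.
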